4.3 Exclusion Criteria

Patients who meet any of the following criteria will be excluded from the study:

[figure not shown]
1. Previously treated or current brain metastases
2. Untreated spinal cord compression. Participants must be neurologically stable off steroids for at least 4 weeks prior to first dose of study drug
3. Ongoing treatment with anti-tumor necrosis factor (TNF) alpha therapies, systemic corticosteroids (prednisone dose $> 10 \text{ mg per day or equivalent}$), or other immune suppressive drugs
4. History of or known or suspected autoimmune disease (exception(s): patients with vitiligo, resolved childhood atopic dermatitis, hypothyroidism, or hyperthyroidism that is clinically euthyroid at Screening are allowed)

5. History of clinically significant cardiovascular disease such as symptomatic congestive heart failure (CHF), uncontrolled hypertension defined as sustained BP >150 mmHg systolic, or >100 mmHg diastolic despite optimal antihypertensive treatment (BP must be controlled at screening), unstable angina pectoris, clinically-significant cardiac arrhythmias, history of stroke (including TIA, or other ischemic event) within 6 months before first dose of study drug, myocardial infarction within 6 months before first dose of study drug, history of thromboembolic event within 3 months before first dose of study drug
6. Known active or chronic hepatitis B or hepatitis C as demonstrated by hepatitis B surface antigen (HBsAg) positivity and/or anti-hepatitis C virus (HCV) positivity, respectively, or known history of human immunodeficiency virus (HIV) seropositive status
7. Clinically active liver disease, including liver cirrhosis of Child-Pugh class B or C
8. Second primary malignancy that has not been in remission for greater than 3 years. Exceptions that do not require a 3-year remission: non-melanoma skin cancer, resected melanoma in situ, or non-muscle invasive urothelial carcinoma
9. In the judgment of the Investigator, patient has a clinically significant concurrent illness or psychological, familial, sociological, geographical, or other concomitant condition that would not permit adequate follow-up and compliance with the study protocol

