5.8 Concomitant Therapy

5.8.1 *Permitted Medications*

In addition to premedications (Section 5.1.4), the following medications may be administered during the study:

- Palliative and supportive care for disease related symptoms
- Granulocyte colony stimulating factors after first dose
- Primary prophylaxis of diarrhea, nausea, and vomiting after first dose
- Anti-inflammatory or narcotic analgesic
- Acute emergency and short-term administration, topical applications, inhaled sprays, eye drops, or local injections of corticosteroids
- Limited palliative radiotherapy
- Caution with any surgical procedures during the study (i.e., if there is clinical indication for surgical procedure during the study this should be discussed with the Sponsor Medical Monitor)

5.8.2 *Prohibited Medications*

The following medications are prohibited during the study:

- Anticancer treatment including chemotherapy, hormonal therapy initiated during the course of the study, radiotherapy, or experimental anticancer medications. Palliative external radiation (e.g., to bone metastasis) is allowed if medically unavoidable. If radiation therapy is required, interruption and/or continuation of study treatment should be discussed with the Medical Monitor
- Chronic, systemic corticosteroid use (prednisone >10 mg/day or equivalent) for palliative or supportive purposes. If treatment with high dose corticosteroids is required for management of AE, interruption and/or continuation of study treatment should be discussed with the Medical Monitor.
- Live vaccine administration during the study, including the treatment period, and until recovery of B lymphocytes to normal ranges following last treatment cycle

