6.22 Prior and Concomitant Medication Data

All prior medications (within 28 days prior to Day 1) and any ongoing or concomitant medications from Day 1 through the SFU (28 days [+ 7 days] after the last study treatment) are to be recorded.

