14.3.2.14	Summary of Treatment Emergent Adverse Events Related to HPN424 That Lead to HPN424 Dose Modifications by System Organ Class and Preferred Term
14.3.2.15	Summary of Dose Limiting Toxicity (DLT) Adverse Events by System Organ Class and Preferred Term
14.3.2.16	Summary of CRS Signs and Symptoms by Preferred Term (From CRS Symptom CRF)
14.3.2.17	Summary of IRR Signs and Symptoms by Preferred Term (From CRS Symptom CRF)

Table Number	Description
14.3.3	Summary of Deaths
14.3.4.1	Safety Laboratory Assessment Shift Table – Serum Chemistry Change from Baseline to Maximum Post-Baseline NCI CTCAE Grade
14.3.4.2	Safety Laboratory Assessment Shift Table – Hematology Change from Baseline to Maximum Post-Baseline NCI CTCAE Grade
14.3.4.3	Safety Laboratory Assessment Shift Table – Coagulation Change from Baseline to Maximum Post-Baseline NCI CTCAE Grade
14.3.4.4	Safety Laboratory Assessment Summary of Patients with Post-Baseline NCI CTCAE Grade 3 or Higher
14.3.5	Summary of 12-Lead Electrocardiogram Abnormalities and Potential QTcF Interval Prolongation
14.3.6	Study Drug Exposure and Compliance

Table of Contents - Listings

Listing Number	Description
16.2.1	Patient Disposition
16.2.2	Patient Enrollment and Eligibility (Inclusion / Exclusion)
16.2.3	Protocol Deviations
16.2.4.1	Demographics
16.2.4.2	Prostate Cancer Medical History
16.2.4.3	Prior Anticancer Therapy
16.2.4.4	Prior Radiation Therapy
16.2.4.5	Prior Prostate Cancer-related Surgery
16.2.4.6	Medical History
16.2.5.1	HPN424 Administration
16.2.5.2	HPN424 Infusion Interruptions
16.2.5.3	Hospital Admission
16.2.6.1	Overall Efficacy Endpoints
16.2.6.2	Radiographic Scans
16.2.6.3	Target Lesions
16.2.6.4	Non-target Lesions
16.2.6.5	New Lesions
16.2.6.6	Bone Scan Assessment
16.2.6.7	Overall Disease Assessment

Listing Number	Description
16.2.6.8	PSA Results
16.2.7.1	Adverse Events
16.2.7.2	Serious Adverse Events
16.2.7.3	Dose-limiting Toxicities
16.2.7.4	Adverse Events Leading to Treatment Discontinuation
16.2.7.5	Adverse Events Leading to HPN424 Dose Modifications
16.2.7.6	Fatal Adverse Events
16.2.7.7	Cytokine Release Syndrome / Infusion Related Reactions Symptoms
16.2.7.8	Deaths
16.2.8.1	Laboratory Results: Hematology
16.2.8.2	Laboratory Results: Chemistry and Testosterone
16.2.8.3	Laboratory Results: Coagulation
16.2.8.4	Laboratory Results: Urinalysis
16.2.8.5	NCI CTCAE Grade 3 or Higher Laboratory Results
16.2.8.6	Patients who had laboratory values that Meet Criteria for Hy's Law

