[8] International Normalized Ratio assumes subjects are not on anticoagulant therapy.

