13.4 NCI CTCAE v5.0 Laboratory Toxicity Grading

Lab Test (CTCAE Term)	Increase / Decrease	Grade 1	Grade 2	Grade 3	Grade 4
Hematology					
WBC (leukocytosis)	Increase	---	---	>100,000 /mm3	---
WBC (decreased)	Decrease	<LLN – 3000 /mm3 <LLN – 3.0 10^9/L	<3000 – 2000 /mm3 <3.0 – 2.0 10^9/L	<2000 – 1000 /mm3 <2.0 – 1.0 10^9/L	<1000 /mm3 <1.0 10^9/L
ANC (decreased)	Decrease	<LLN – 1500 /mm3 <LLN – 1.5 10^9/L	<1500 – 1000 /mm3 <1.5 – 1.0 10^9/L	<1000 – 500 /mm3 <1.0 – 0.5 10^9/L	<500 /mm3 <0.5 10^9/L
Lymphocytes (increased)	Increase	---	>4000 – 20,000 /mm3	>20,000 /mm3	---
Lymphocytes (decreased)	Decrease	<LLN – 800 /mm3 <LLN – 0.8 10^9/L	<800 – 500 /mm3 <0.8 – 0.5 10^9/L	<500 – 200 /mm3 <0.5 – 0.2 10^9/L	<200 /mm3 <0.2 10^9/L
Eosinophils (eosinophilia)	Increase	> ULN and > BL	---	---	---
Hemoglobin (anemia)	Decrease	<LLN – 10 g/dL <LLN – 6.2 mmol/L <LLN – 100 g/L	<10 – 8 g/dL <6.2 – 4.9 mmol/L <100 – 80 g/L	<8 g/dL <4.9 mmol/L <80 g/L	---
Hemoglobin (increased) [1]	Increase	>0 – 2 g/dL above ULN or above BL if BL is > ULN	>2 – 4 g/dL above ULN or above BL if BL is > ULN	>4 g/dL above ULN or above BL if BL is > ULN	---
Platelets (decreased)	Decrease	<LLN – 75,000 /mm3 <LLN – 75.0 10^9/L	<75,000 – 50,000 /mm3 <75.0 – 50.0 10^9/L	<50,000 – 25,000 /mm3 <50.0 – 25.0 10^9/L	<25,000 /mm3 <25.0 10^9/L
Coagulation					
APTT (prolonged)	Increase	>ULN – 1.5x ULN	>1.5 – 2.5x ULN	>2.5x ULN	---
INR (increased)	Increase	>1.2 – 1.5	>1.5 – 2.5	>2.5	---
Chemistry					
ALT (increased)	Increase	>ULN – 3.0x ULN if BL was normal 1.5 – 3.0x BL if BL was abnormal	>3.0 – 5.0x ULN if BL was normal >3.0 – 5.0x BL if BL was abnormal	>5.0 – 20.0x ULN if BL was normal >5 – 20.0x BL if BL was abnormal	>20.0x ULN if BL was normal >20.0x BL if BL was abnormal

Lab Test (CTCAE Term)	Increase / Decrease	Grade 1	Grade 2	Grade 3	Grade 4
AST (increased)	Increase	>ULN – 3.0x ULN if BL was normal 1.5 – 3.0x BL if BL was abnormal	>3.0 – 5.0x ULN if BL was normal >3.0 – 5.0x BL if BL was abnormal	>5.0 – 20.0x ULN if BL was normal >5 – 20.0x BL if BL was abnormal	>20x ULN if BL was normal >20.0x BL if BL was abnormal
ALK PHOS (increased)	Increase	>ULN – 2.5x ULN if BL was normal 2.0 – 2.5x BL if BL was abnormal	>2.5 – 5.0x ULN if BL was normal >2.5 – 5.0x BL if BL was abnormal	>5.0 – 20.0x ULN if BL was normal >5.0 – 20.0x BL if BL was abnormal	>20.0x ULN if BL was normal >20.0x BL if BL was abnormal
LDH (increased)	Increase	>ULN	---	---	---

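### INR is graded as if no patient takes an anticoagulant, but nothing in the protocol makes that true, so anticoagulant-driven values are tabulated as Grade 2 or 3

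*SAP*

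**What the plan says.** SAP 13.3 attaches footnote [8] to the INR row: "International Normalized Ratio assumes subjects are not on anticoagulant therapy". The grading row in SAP 13.4 reads "INR (increased) Increase >1.2 – 1.5 >1.5 – 2.5 >2.5", with no Grade 4 and no reference to baseline. The aPTT row reads "APTT (prolonged) Increase >ULN – 1.5x ULN >1.5 – 2.5x ULN >2.5x ULN" and has no footnote about anticoagulants. In the same table the liver tests have a second branch for patients who enter with an abnormal value, for example Grade 1 ALT at "1.5 – 3.0x BL if BL was abnormal".

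SAP 10.5 grades on the numeric result alone, without clinical interpretation. The grades feed the coagulation shift table (14.3.4.3, baseline to maximum post-baseline grade), Table 14.3.4.4, titled "Safety Laboratory Assessment Summary of Patients with Post-Baseline NCI CTCAE Grade 3 or Higher", and Listing 16.2.8.5. SAP 8.6 reports prior and concomitant medication in listings only.

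On the protocol side, the closest exclusion (Section 4.3, no. 5) includes "history of thromboembolic event within 3 months before first dose of study drug". Section 5.8.2 opens "The following medications are prohibited during the study" and names anticancer treatment, chronic systemic corticosteroids and live vaccines. Section 6.22 requires sites to record "any ongoing or concomitant medications from Day 1 through the SFU".

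**The concern.** The SAP recognises that anticoagulation changes what an INR means, then assumes it away, and no rule in the protocol backs the assumption. A patient with an older thromboembolic event may enter on an anticoagulant, and any patient may start one during the study. The raised INR that follows is intended, yet it is graded and tabulated like a drug-induced abnormality.

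This deserves attention because the study stopped in Part 1 and the report is a synoptic one centred on safety (SAP 3). Laboratory abnormalities are among the few endpoints it still summarises (SAP 4.4). Coagulation results also have some bearing on this drug: Protocol 5.4.1 names disseminated intravascular coagulation as a possible complication of cytokine release syndrome, and Protocol 5.4.3 lists PT/PTT/INR among the tests to consider when transaminases rise. Grades produced by an anticoagulant would make a real signal harder to see.

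**Working it through.** The plan states no figure on this point, so there is none to reproduce. The check has three steps.

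**1. Does any rule make the assumption true?**
- Eligibility (Protocol 4.2, 4.3): no criterion names anticoagulants, and there is no INR or PTT entry limit. Thromboembolic events more than 3 months old are not excluded.
- Medication rules (Protocol 5.8.1, 5.8.2): anticoagulants are neither listed as permitted nor prohibited.
- SAP 10.5, 13.3 and 13.4: no rule flags, excludes or regrades an anticoagulated patient.

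**2. What grade results?** The SAP 13.4 cut-offs were applied to INR in steps of 0.1, the reporting precision in SAP 13.3. The documents give no therapeutic range, so three are assumed.

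| Assumed INR range | Values | Grade 1 | Grade 2 | Grade 3 |
|---|---|---|---|---|
| 1.5–2.0 | 6 | 1 | 5 | 0 |
| 2.0–3.0 | 11 | 0 | 6 | 5 |
| 2.5–3.5 | 11 | 0 | 1 | 10 |

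Whatever the range, a value above 1.5 is Grade 2 and a value above 2.5 is Grade 3.

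For aPTT, take the SAP 13.3 textbook upper limit of 35 s, used only when the local range is missing. Grade 2 starts above 1.5 × 35 = 52.5 s and Grade 3 above 2.5 × 35 = 87.5 s, whether or not the patient is on an anticoagulant.

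**3. Where does the grade appear?** Three illustrative patients (INR values assumed):
- Starts an anticoagulant on study, INR 1.0 then 2.6. Table 14.3.4.3 shows Grade 0 to Grade 3, and the patient is counted in Table 14.3.4.4.
- Anticoagulated at entry, INR 2.3 then 2.6. Table 14.3.4.3 shows Grade 2 to Grade 3, and the patient is counted in Table 14.3.4.4. Yet 2.6/2.3 = 1.13 times baseline.
- Anticoagulated and stable, INR 2.8 throughout. Table 14.3.4.3 shows Grade 3 to Grade 3, so no shift. If the title of Table 14.3.4.4 is taken literally, the patient is still counted there.

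The shift table takes the maximum over Day 1 draws of successive cycles, so a single value above 2.5 is enough. How often that happens cannot be derived from the documents. A patient held at 2.2 never reaches Grade 3 (0%). If draws were independent and uniform over 2–3, the chance of at least one Grade 3 in k draws would be 1 − 0.5^k: 50% for k = 1, 88% for k = 3 and 97% for k = 5. The truth for a given patient may lie anywhere in that range.

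**The case against.** The best defence is that the convention is disclosed. SAP 10.5 says grading is numeric only, footnote [2] in SAP 13.3 sends clinical assessment to adverse event reporting, and every table with laboratory grades must point to SAP 13.3 and 13.4. Footnote [7] makes a similar simplification for fasting glucose. The listings would let a reader match INR values to medication. This limits the harm, but a pointer does not correct the tabulated grade, and no table identifies anticoagulated patients.

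Several stronger readings are tempting, and the documents do not support them:
- A reader might infer that footnote [8] also covers aPTT. It is attached to INR only. For aPTT the gap is a missing branch, not a stated assumption.
- A reader might infer that recent thromboembolism is the only cardiovascular bar, or that the protocol expressly admits anticoagulated patients. Exclusion 5 also bars clinically significant arrhythmias, unstable angina, and stroke or myocardial infarction within 6 months, so the eligible pool is narrower. Admission is inferred from silence.
- A reader might infer that every anticoagulated patient shows a false shift. Those stable at entry do not, because the shift table displays their baseline grade.
- A reader might want a number of spurious Grade 3 patients. The documents give no prevalence of anticoagulant use, no drug type and no INR target, so any count would be assumption throughout.
- A reader might infer an effect on dosing. Dose-limiting toxicities follow separate criteria (Protocol 5.2) and are reviewed by the Cohort Review Committee (Protocol 11.9). These tables play no part.

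It is also fair that the reading of Table 14.3.4.4 rests on its title, since the SAP gives no shell or derivation.

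**Conclusion.** The point holds as a reporting defect in the coagulation grades. The SAP states an assumption that the protocol does not secure, and its cut-offs then mechanically turn an anticoagulant-driven INR above 1.5 into Grade 2 and above 2.5 into Grade 3. The same gap exists, unstated, for aPTT. The effect is concentrated in Table 14.3.4.4 and, in Table 14.3.4.3, among patients who start an anticoagulant or cross a cut-off on study.

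That conclusion rests on the absence of any anticoagulant rule in either document and on a literal reading of the Table 14.3.4.4 title. How far grades rise within a therapeutic range depends on the assumed ranges shown above. The number of patients affected is unknown and could be small. It should be corrected before the tables are produced, because the report is chiefly about safety and the correction needs no new data.

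**What to change.** Replace the assumption in footnote [8] with a rule:

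1. Flag anticoagulant use at each INR and aPTT draw. Medications are recorded through safety follow-up (Protocol 6.22) and coded to the ATC classification (SAP 8.6).
2. For patients anticoagulated at baseline, grade INR as a multiple of their own baseline, as the SAP already does for ALT, AST, ALP and bilirubin. The steps could be 1.5 and 2.5 times baseline. With a baseline of 2.3, Grade 2 would start above 1.5 × 2.3 = 3.45 and Grade 3 above 2.5 × 2.3 = 5.75. State which baseline grade the shift table shows for these patients, so that an absolute baseline grade set against a relative post-baseline grade does not look like improvement.
3. For patients who start an anticoagulant on study, keep their values in the tables. Removing them could hide true coagulopathy, particularly if the drug was started because of an on-study event.
4. Present Tables 14.3.4.3 and 14.3.4.4 with and without flagged patients, state the rule in a table footnote, and carry the flag into Listings 16.2.8.3 and 16.2.8.5.

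The cost is a small added derivation, a review of the coded medication terms, and one extra display.

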13.4 NCI CTCAE v5.0 Laboratory Toxicity Grading

Lab Test (CTCAE Term)	Increase / Decrease	Grade 1	Grade 2	Grade 3	Grade 4
Hematology					
WBC (leukocytosis)	Increase	---	---	>100,000 /mm3	---
WBC (decreased)	Decrease	<LLN – 3000 /mm3 <LLN – 3.0 10^9/L	<3000 – 2000 /mm3 <3.0 – 2.0 10^9/L	<2000 – 1000 /mm3 <2.0 – 1.0 10^9/L	<1000 /mm3 <1.0 10^9/L
ANC (decreased)	Decrease	<LLN – 1500 /mm3 <LLN – 1.5 10^9/L	<1500 – 1000 /mm3 <1.5 – 1.0 10^9/L	<1000 – 500 /mm3 <1.0 – 0.5 10^9/L	<500 /mm3 <0.5 10^9/L
Lymphocytes (increased)	Increase	---	>4000 – 20,000 /mm3	>20,000 /mm3	---
Lymphocytes (decreased)	Decrease	<LLN – 800 /mm3 <LLN – 0.8 10^9/L	<800 – 500 /mm3 <0.8 – 0.5 10^9/L	<500 – 200 /mm3 <0.5 – 0.2 10^9/L	<200 /mm3 <0.2 10^9/L
Eosinophils (eosinophilia)	Increase	> ULN and > BL	---	---	---
Hemoglobin (anemia)	Decrease	<LLN – 10 g/dL <LLN – 6.2 mmol/L <LLN – 100 g/L	<10 – 8 g/dL <6.2 – 4.9 mmol/L <100 – 80 g/L	<8 g/dL <4.9 mmol/L <80 g/L	---
Hemoglobin (increased) [1]	Increase	>0 – 2 g/dL above ULN or above BL if BL is > ULN	>2 – 4 g/dL above ULN or above BL if BL is > ULN	>4 g/dL above ULN or above BL if BL is > ULN	---
Platelets (decreased)	Decrease	<LLN – 75,000 /mm3 <LLN – 75.0 10^9/L	<75,000 – 50,000 /mm3 <75.0 – 50.0 10^9/L	<50,000 – 25,000 /mm3 <50.0 – 25.0 10^9/L	<25,000 /mm3 <25.0 10^9/L
Coagulation					
APTT (prolonged)	Increase	>ULN – 1.5x ULN	>1.5 – 2.5x ULN	>2.5x ULN	---
INR (increased)	Increase	>1.2 – 1.5	>1.5 – 2.5	>2.5	---
Chemistry					
ALT (increased)	Increase	>ULN – 3.0x ULN if BL was normal 1.5 – 3.0x BL if BL was abnormal	>3.0 – 5.0x ULN if BL was normal >3.0 – 5.0x BL if BL was abnormal	>5.0 – 20.0x ULN if BL was normal >5 – 20.0x BL if BL was abnormal	>20.0x ULN if BL was normal >20.0x BL if BL was abnormal

Lab Test (CTCAE Term)	Increase / Decrease	Grade 1	Grade 2	Grade 3	Grade 4
AST (increased)	Increase	>ULN – 3.0x ULN if BL was normal 1.5 – 3.0x BL if BL was abnormal	>3.0 – 5.0x ULN if BL was normal >3.0 – 5.0x BL if BL was abnormal	>5.0 – 20.0x ULN if BL was normal >5 – 20.0x BL if BL was abnormal	>20x ULN if BL was normal >20.0x BL if BL was abnormal
ALK PHOS (increased)	Increase	>ULN – 2.5x ULN if BL was normal 2.0 – 2.5x BL if BL was abnormal	>2.5 – 5.0x ULN if BL was normal >2.5 – 5.0x BL if BL was abnormal	>5.0 – 20.0x ULN if BL was normal >5.0 – 20.0x BL if BL was abnormal	>20.0x ULN if BL was normal >20.0x BL if BL was abnormal
LDH (increased)	Increase	>ULN	---	---	---
Total Bilirubin (increased)	Increase	>ULN – 1.5x ULN if BL was normal >1.0 – 1.5x BL if BL was abnormal	>1.5 – 3.0x ULN if BL was normal >1.5 – 3.0x BL if BL was abnormal	>3.0 – 10.0x ULN if BL was normal >3.0 – 10.0x BL if BL was abnormal	>10x ULN if BL was normal >10.0x BL if BL was abnormal
Albumin (hypoalbuminemia)	Decrease	<LLN – 3.0 g/dL <LLN – 30 g/L	<3 – 2 g/dL <30 – 20 g/L	<2 g/dL <20 g/L	---
Creatinine (increased)	Increase	>ULN – 1.5x ULN	>1.5 – 3.0x ULN or >1.5 – 3.0x BL	>3.0 – 6.0x ULN or >3.0x BL – 6.0x ULN	>6.0x ULN
Glucose (hypoglycemia)	Decrease	<LLN – 55 mg/dL <LLN – 3.0 mmol/L	<55 – 40 mg/dL <3.0 – 2.2 mmol/L	<40 – 30 mg/dL <2.2 – 1.7 mmol/L	<30 mg/dL <1.7 mmol/L
Lipase (increased)	Increase	>ULN – 1.5x ULN	>1.5 – 2.0x ULN	>2.0 – 5.0x ULN	>5.0x ULN
Amylase (increased)	Increase	>ULN – 1.5x ULN	>1.5 – 2.0x ULN	>2.0 – 5.0x ULN	>5.0x ULN
Corrected Calcium (hypercalcemia) [2]	Increase	>ULN – 11.5 mg/dL >ULN – 2.9 mmol/L	>11.5 – 12.5 mg/dL >2.9 – 3.1 mmol/L	>12.5 – 13.5 mg/dL >3.1 – 3.4 mmol/L	>13.5 mg/dL >3.4 mmol/L
Corrected Calcium (hypocalcemia) [2]	Decrease	<LLN – 8.0 mg/dL <LLN – 2.0 mmol/L	<8.0 – 7.0 mg/dL <2.0 – 1.75 mmol/L	<7.0 – 6.0 mg/dL <1.75 – 1.5 mmol/L	<6.0 mg/dL <1.5 mmol/L
Potassium (hyperkalemia)	Increase	>ULN – 5.5 mmol/L	>5.5 – 6.0 mmol/L	>6.0 – 7.0 mmol/L	>7.0 mmol/L

Lab Test (CTCAE Term)	Increase / Decrease	Grade 1	Grade 2	Grade 3	Grade 4
Potassium (hypokalemia)	Decrease	--	<LLN – 3.0 mmol/L	<3.0 – 2.5 mmol/L	<2.5 mmol/L
Magnesium (hypermagnesemia)	Increase	>ULN – 3 mg/dL >ULN – 1.23 mmol/L	---	>3 – 8 mg/dL >1.23 – 3.30 mmol/L	>8.0 mg/dL >3.30 mmol/L
Magnesium (hypomagnesemia)	Decrease	<LLN – 1.2 mg/dL <LLN – 0.5 mmol/L	<1.2 – 0.9 mg/dL <0.5 – 0.4 mmol/L	<0.9 – 0.7 mg/dL <0.4 – 0.3 mmol/L	<0.7 mg/dL <0.3 mmol/L
Sodium (hypernatremia)	Increase	>ULN – 150 mmol/L	>150 – 155 mmol/L	>155 – 160 mmol/L	>160 mmol/L
Sodium (hyponatremia)	Decrease	<LLN – 130 mmol/L	---	120 - <130 mmol/L	<120 mmol/L
Uric Acid (increased)	Increase	---	---	> ULN	---

[1] For hemoglobin grading, in order to maintain the intention of CTCAE v4.03, the assumption is made that grading for increased levels are compared to ULN if baseline result is within normal range, or above baseline if baseline is above ULN.

[2] Serum calcium is corrected for albumin to assign CTCAE Grade; corrected calcium is derived as follows:

$$\text{corrected-CA (mmol/L)} = \text{serum-CA (mmol/L)} + 0.020 * (40 - \text{albumin (g/L)})$$
